11.4 Database management

Paper CRF data will be entered by trained member(s) of the research team at site into a commercially available web based CDMS provided by the LCTU. On-entry validation checks will be applied where required and data entered will be checked for completeness, accuracy and timeliness by the trial team/trial manager/data manager, with queries managed using the data clarification functionality within the CDMS system.

The contacts database (which contains participant contact details) will be held separately from the trial database. This will be password protected and managed at site by the research team following their usual clinical practice.

A Data Management Plan will be created with specific details on data handing and record keeping.

11.5 Archiving

Personal identifiable data generated by the trial will be retained for the minimum time determined by the regulatory authorities following the notification of the end of the trial before being destroyed in a confidential manner.

Following completion of the trial data analysis, data and essential trial records, including the final trial report, will be archived in a secure location, for at least 25 years after the completion of the trial, in accordance with EU regulations. No trial-related records, including hospital medical notes, will be destroyed unless or until the Sponsor gives authorisation to do so.

12 MONITORING, AUDIT & INSPECTION

The University of Leicester, as Sponsor, operates a risk-based monitoring and audit programme, to which this trial will be subject. The LCTU operates a risk-based Quality Management System which will apply to this trial with Quality Checks and Quality Assurance Audits performed as required.

Regular monitoring will be performed according to ICH GCP. Data will be evaluated for compliance with the protocol and accuracy in relation to source documents. Following written standard operating procedures, the monitors will verify that the clinical trial is conducted and data are generated, documented and reported in compliance with the protocol, GCP and the applicable regulatory requirements.

As part of the quality management process, the trial will be subject to a risk assessment and a monitoring plan will be developed by the Sponsor in accordance with the level of risk identified to participant safety, integrity of the trial and trial data validity. All trial monitoring will be conducted in accordance with the monitoring plan and will be undertaken by the trial Sponsor. All monitoring will be performed by staff who are ICH/GCP trained and are competent in monitoring to all applicable regulatory guidelines. A documented monitoring log and audit trail will be maintained throughout the lifetime of the trial. The trial may also be subject to audit by the Sponsor delegate.

The trial manager will also undertake quality checks and assurance audits to ensure compliance with protocol, ICH GCP and regulatory requirements.

All source data, trial documents, and participant notes will be made available for monitoring, audits and inspections by the Sponsor (or their delegate), NHS Host Organisation and the regulatory authorities.

13 ETHICAL AND REGULATORY CONSIDERATIONS

13.1 Research Ethics Committee (REC) review & reports

Before the start of the trial, approval will be sought from a REC for the trial protocol, informed consent forms and other relevant documents e.g. advertisements. Any substantial amendments that require review by REC will not be implemented until the REC grants a favourable opinion for the trial.

All correspondence with the REC will be retained in the Trial Master File/Investigator Site File and an annual progress report (APR) will be submitted to the REC by CI within 30 days of the anniversary date on which the favourable opinion was given, and annually until the trial is declared ended. The CI will also be responsible for informing the REC of the end of trial. After completion of the trial, CI will submit a final report with the results to the REC.

13.2 Peer review

The trial has been reviewed by the Genentech Respiratory Group including clinicians and senior scientists. This review team have had the protocol reviewed by their internal senior management and approved for support.

13.3 Public and Patient Involvement

Through the NIHR BRC the trial design has been discussed by our patient involvement team within the BRC Respiratory Theme and across the wider BRC PPI group. This group will also be sent copies of the participant documentation for review. We will also invite several members of this group to act as lay committee members on the Trial Steering Committee, for which we will provide expense payments.

13.4 Regulatory Compliance

The trial will not commence until Clinical Trial Authorisation (CTA) is obtained from MHRA and REC and Sponsor Green Light has been issued. The protocol and trial conduct will comply with the Medicines for Human Use (Clinical Trials) Regulations 2004 and any relevant amendments. As the participants may have a non-contrast CT scan and Chest X-Ray at the start and end of trial, the procedures are compliant with the Ionising Radiation (Medical Exposure) Regulations.

The trial will be conducted in accordance with the UK Policy Framework for Health and Social Care Research (2017) and the Medicines for Human Use (Clinical Trials) Regulations, 2004. The

Sponsor responsible for checking research governance arrangements will be the University of Leicester.

13.5 Known and Potential Benefits to Participants

For those participants that will be randomised to receive Anti-ST2 they may experience a reduction in exacerbations and an overall improvement in COPD. Those participants receiving the placebo may also experience the placebo effect in which the expectation of receiving treatment can result in health improvements.

For all participants participation in this trial will help by making a significant contribution to research into COPD and will improve management of patients in the future. During the trial all participants will receive close monitoring of their COPD and attention to ensure that they are receiving the optimal medical treatment. Any exacerbations would also be investigated and followed up by the trial team. Any abnormal findings arising from the trial procedures that are considered clinically significant by the trial team will be reported to the GP for further investigation.

Participants will be reimbursed for the inconvenience and burden of the trial visit schedule and due to the moderately higher than standard care risk of participation (see section 7.1.3)

13.6 Known and Potential Risk to Participants

The trial is as low risk as the Investigators can make it. Although some of the appointments with the full testing maybe fairly long (~half day), therefore participants will be offered a break and refreshments provided.

There is a possibility that a temporary halt or change to medications may cause worsening of symptoms. These will be adjusted at clinical review and revised where necessary.

Both the placebo and trial drug can potentially cause local reactions (e.g. rash, inflammation). Anti-ST2 may reduce exacerbation risk and symptoms and therefore might offer beneficial effects. The safety profile for this drug is considered good with a slightly higher risk than the patient would receive from standard care, based on the previous asthma studies that have been conducted at this time.

The effects and discomforts of each individual test are detailed in the Patient Information Leaflet (PIL) and described briefly below:

- Non Contrast CT Scan (Chest) This is a painless procedure. The CT scan exposes
 patients to ionising radiation, which has theoretical risks to health. However the dose
 received (~7 mSv) is comparable to natural background radiation for 2 years, and
 therefore the risks are not considered clinically relevant.
- Chest X-Ray (CXR) This is a painless procedure. The Chest X-ray exposes patients to ionising radiation, which has theoretical risks to health. However the dose received (~0.1 mSv) is comparable to natural background radiation for 10 days, and therefore the risks are not considered clinically relevant.

- Echocardiogram (Echo) This is a safe test utilising ultrasound that some participants will have had before. Patients may notice some mild discomfort when the probe is pressed on their chest but there are no known long term side effects known (takes ~20min).
- Electrocardiogram (ECG) The ECG is a simple painless test, with 10 electrodes used to record 12 different views of the heart's electrical activity. An electrode is attached to each ankle and wrist with sticky pads and six more are attached to the chest. The patient lies almost flat with the head and chest raised a little. Relaxing for a few minutes before the recording is made. Very rarely someone may have a slight skin reaction to the electrodes, but normally there are no after effects.
- **Blood sample** Blood testing may cause some mild discomfort and occasionally some bruising. All samples will be taken by a doctor or fully trained health professional. Each donation of blood will be a 100ml (about 7 tablespoons) maximum per visit.
- **Sputum Collection** involves inhaling a salty solution for three 5-minute periods. This can cause some chest tightness, wheezing and/or cough. These can all readily be reversed by inhaling a bronchodilator (ventolin). In order to monitor this, lung function testing will be performed before and during this test

Breathing tests – Spirometry, PEX (Particle Exhaled) Machine and other breathing tests may cause some temporary light headedness, and coughing. The blowing tests during this procedure may cause airway irritation which will be reversed with Salbutamol if required.

- **Nasal Epithelial Sampling** A small brush or scoop is inserted and gently rubbed inside the nostril (a few seconds) or a small volume of sterile salt solution will be inserted into each nostril, then allowed to run out into a collection pot (several minutes). There may be a little discomfort that induces sneezing, coughing and, rarely, minor bleeding for a short period of time. This sample will be optional.
- **Nasosorption**: A small piece of paper will be inserted into the nostril to collect nasal fluid.

13.6.1 Possible Side Effects of the Trial Medication and the Placebo

Anti-ST2 (MSTT1041A) is being developed by Genentech for the treatment of uncontrolled severe asthma and COPD. Due to its mechanism of action, Anti-ST2 has the ability to block inflammation, prevent exacerbations, and improve lung function and quality of life in both patient populations.

Anti-ST2 is in early clinical development, and the safety profile in humans is not fully known. Anti-ST2 is contraindicated in subjects with known hypersensitivity to the active substance or any of the excipients. Other exclusion criteria are listed in Section 6.2.

Three Phase I studies of Anti-ST2 to provide PK, PD, and safety information over a broad dose range have completed dosing and safety follow-up in all subjects. These include a SAD study (AMG Study 20110235), a MAD study (AMG Study 20110236), and a single-dose PK study in subjects of Japanese heritage (AMG Study 20130177). In the three completed AMG Phase I

studies there were no serious adverse events (SAEs) or adverse events (AEs) that led to treatment discontinuation in healthy subjects from the three completed AMG Phase I studies, who received single SC doses of Anti-ST2 ranging from 2.1-560 mg and IV doses ranging from 210-700 mg.

In the Phase I studies there were no clinically relevant trends in any of the following safety parameters:

- Laboratory abnormalities
- Percent change in vital signs measurements: systolic and diastolic blood pressure, pulse rate, temperature, or respiratory rate
- QTcF interval

Based on preliminary data from these studies, a Phase IIb study was initiated to study patients with uncontrolled severe asthma who are receiving standard asthma therapy. This study is currently ongoing (EudraCT 2016-001549-13, NCT 02918019).

Our trial will be the first looking at Anti-ST2 in COPD. As Anti-ST2 is in early clinical development the full safety profile in humans is not yet known. Please refer to the associated current Investigator's Brochure (IB) which lists the potential known risks and side effects for both the IMP and the placebo.

13.7 Protocol compliance

The trial team will monitor and review protocol compliance, deviations from the protocol will be captured both within the source data and the LCTU Quality Management System. Drug accountability will be monitored throughout the trial period. Where deviations frequently reoccur this may meet the criteria for a Serious Breach of GCP and will be reported in line with Section 13.6.

13.8 Notification of Serious Breaches to GCP and/or the protocol

Any serious breach (a breach which is likely to effect to a significant degree the safety or physical or mental integrity of the participants of the trial; or the scientific value of the trial) will be reported to Sponsor immediately.

13.9 Data protection and patient confidentiality

All investigators and trial site staff will comply with the requirements of relevant legislation with regards to the collection, storage, processing and disclosure of personal information for the University of Leicester, the Leicester Clinical Trials Unit and the local NHS Trusts.

The personal information that is collected will be kept secure and maintained by:

• The creation of a unique participant ID number, depersonalised data where the participant's identifying information is replaced by an unrelated sequence of characters

- Secure maintenance of the data, in both electronic and paper forms and the linking code in separate locations
- limiting access to the minimum number of individuals necessary for quality control, audit, and analysis
- Paper based anonymised trial records will be stored in locked filing cabinets within a locked office. Electronic records will be stored on secure University of Leicester IM&T server systems.
- The database will be password protected and only researchers collecting data will have access. All data collected during the trial will be stored anonymously.
- Participant's contact details will be held separate to the trial visit data and used to arrange data collection visits by the research team or direct care team.
- Any data transmitted will be done securely in approved University of Leicester methods (i.e. encrypted file transfer, internal email system) in accordance with LCTU SOPs.
- •

13.10 Financial and other competing interests for the chief investigator, PIs at each site and committee members for the overall trial management

All real and perceived conflicts will be recorded and reported to the TSC. Members of the TSC and DSMC Committees will be required to sign a declaration of conflicts of interest forms which will be retained in the TMF.

13.11 Indemnity

Sponsorship and insurance for the trial will be provided by the University of Leicester.

If a participant is harmed due to negligence, this would be covered by the local NHS Trust(s) indemnity arrangements for all participants in clinical trials. If a trial participant wishes to make a complaint about any aspects of the way they have been treated or approached during the research project, the standard National Health Service complaint system will be available to them, the contact details for which are in the participant information sheet.

13.12 Amendments

Amendments will be submitted by the PI after approval by the Sponsor and will be implemented following all required ethical, competent authority and Sponsor approvals.

13.13 Post trial care

After the completion of trial participants will be discharged back to the care of their GP and won't be followed up, unless they have had an adverse reaction to IMP.

13.14 Access to the final trial dataset

CI and his appointed deputies will have access to trial dataset.

14 DISSEMINIATION POLICY

14.1 Dissemination policy

A publication plan will be written by the TMG during the trial with the sponsor and funder approvals. It is envisaged that the results of the trial will be published in the relevant peer-reviewed journals. Acknowledgement of any supporting organisations, including funders, University of Leicester and the LCTU, will be included.

16. APPENDICES

Appendix 1: Schedule of Procedures Appendix 2: Amendment History Appendix 3: Participant Trial Flow Chart

Page 47 of 60

16.1 Appendix 1 – Schedule of Procedures

Trial	Screen	Ran	domise	ed treat	tment ((visit w	vindow	+/- 7 c	lays)					Efficacy end point	3 month post-trial follow-up	Withdrawal	Unscheduled visit (e.g.
assessment	V0	V1	V2	V3	V4	V5	V6	V7	V8	V9	V 10	V 11	V 12	V13 +/-7 days	V14 +/-14 days		exacerbation)
		Wk 0	Wk 4	Wk 8	Wk 12	Wk 16	Wk 20	Wk 24	Wk 28	Wk 32	Wk36	Wk40	Wk44	Wk 48	Wk 60		
Consent	х												_				
Review Inclusion & Exclusion	х	x	x	x	х	х	x	x	x	x	Х	X	X	Х	x	×♦	×♦
Randomisation		х									/	ļ.					
Dosing		х	х	х	х	х	Х	Х	х	Х	X	X	х				
Demographics (age, gender, BMI, ethnicity, smoking status)	x																
Vital signs (pulse, BP, temp, O₂ sats)	x	x	x	x	х	х	х	x	X	х	Х	Х	Х	XV	X^	×♦	×♦
Medical history	х																
Concomitant Med	х	х	х	х	х	Х	X	X	Х	Х	Х	Х	х	X	х	×♦	X♦
Physical examination	Х	х					,								X^		×♦
Safety AE/SAE		Х	х	х	х	X	Х	Х	Х	Х	Х	Х	Х	Х	Х	X♦	x♦
COPD ⁺⁺ Exacerbation frequency			Х	x	x	x	х	х	Х	Х	X	X	X	x	x		×♦
SGRQ-c		Х	х		х			Х			Х			Х^	X^	X♦	x♦
mMRC	Х	Х	Х		Х			Х			х			Х^	Х^	X♦	x•
CAT		Х	X		Х			Х			Х			Х^	X^	X♦	x•
VAS (dyspnoea, cough, sputum)		х	x		х			Х			Х			X^	Х^	×♦	×♦
Sputum Purulence Colour Card	Х				х			х			Х			X^	X^	X♦	X.

Page **48** of **60**

Anti-ST2 in COPD Protocol

EudraCT: 2018-000919-24

Trial	Screen	Rano	domise	ed treat	tment	(visit w	vindow	+/- 7 c	lays)					Efficacy end point	3 month post-trial follow-up	Withdrawal	Unscheduled visit (e.g.
assessment	V0	V1	V2	V3	V4	V5	V6	V7	V8	V9	V 10	V 11	V 12	V13 +/-7 days	V14 +/-14 days		exacerbation)
		Wk 0	Wk 4	Wk 8	Wk 12	Wk 16	Wk 20	Wk 24	Wk 28	Wk 32	Wk36	Wk40	Wk44	Wk 48	Wk 60		
VOC (PTRMS & ADVION)	x				х			х			x			x^	x^		x•
Post- BD spirometry	х		х		х			х			х			x^	x^	X♦	X♦
Pre and post BD spirometry		х												x^			
'Body box'	X ⁺													x^			
HbA ₁ c	х		х		Х			Х			х			x^	x^		×♦
FBC	х		х		х			Х			Х			x^	x^	X\$	X♦
U&Es	х		х		Х			Х			х			x^	x^	X\$	X♦
LFTs	х		х		Х			Х			х			x^	x^	X\$	x♦
CRP	х		х		Х			Х			х			x^	x^	X\$	x♦
RNA (PAXgene)	х		х		Х			Х			Х			x^	x^	X\$	X♦
DNA (PAXgene)	х																
Total IgE & RAST (HDM, pollen, cat, dog)	x																
Serum/plasma inflam biomarkers	x		x		х			х			х			x^	x^	X♦	×♦
Lipid profile	х													x^			
Pharmacokinetic s PK ^{\$}		х	х					х						x^			X♦
ADA		х	х					х						x^			X♦
Pharmacogeneti cs SNPs	x													x^			
NTproBNP	х		х		х			х			х			x^	x^	X\$	X♦
Participant Diary		Х	х	Х	Х	х	х	Х	Х	Х	Х	х	х	х	Х	X\$	X♦

Page **49** of **60**

Trial	Screen	Rano	domise	ed treat	tment	(visit w	indow	+/- 7 c	lays)					Efficacy end point	3 month post-trial follow-up	Withdrawal	Unscheduled visit
assessment	V0	V1	V2	V3	V4	V5	V6	V7	V8	V9	V 10	V 11	V 12	V13 +/-7 days	V14 +/-14 days		(e.g. exacerbation)
		Wk 0	Wk 4	Wk 8	Wk 12	Wk 16	Wk 20	Wk 24	Wk 28	Wk 32	Wk36	Wk40	Wk44	Wk 48	Wk 60		
Urine sample (10-20ml) for Inflam Biomarker	x	x	x		x			x			Х			Х^	X^	X♦	X♦
Sputum for Biomarkers Differential cell count, qPCR and Microbiome		x	x		x			x			x			X^	X^		X♦
Nasal epithelial sampling & nasosorption	x				х			х			X			X^	x^		×♦
Pregnancy Testing **	х	х	х	х	х	Х	х	х	Х	х	х	Х	х	X^	x^	X♦	×♦
ECG [£]	х													Х^			X♦
ECHO*		Х															X♦
CXR																	×♦
Non-contrast CT chest ^{\$\$}	x													X^			

* For clinically meaningful increase in NTproBNP **OR** new symptoms/signs concerning for HF or cardiac dysfunction **OR** clinically significant ECG changes from baseline

+ Body plethysmography ('body box') will be done anytime between screening and week 12, unless patient has had the test within 12 months prior to screening

\$ Pk samples should be taken pre-dose

£ 12 lead ECG. If, in the opinion of investigator, the ECG is grossly abnormal (e.g. LBBB, prolonged QTc), it will be compared to old ECGs. If there are no old ECGs for comparison, the investigator will make a clinical judgement about the suitability of the patients to take part in trial.

\$\$ CT scan. Patients who are claustrophobic or unable to lie flat won't be offered CT scan.

++ COPD Exacerbation frequency where a COPD exacerbation is defined by symptomatic worsening of COPD requiring use of systemic corticosteroids for at least 3 days, a single depot injectable dose of corticosteroids will be considered equivalent to a 3-day course of systemic corticosteroids; and/or Use of antibiotics; and/or An inpatient hospitalisation or death due to COPD.

Page **50** of **60**

** Pregnancy testing (blood and urine) can be at any trial visit for WOCBP (i.e.fertile, following menarche and until becoming post-menopausal unless permanently sterile. Permanent sterilisation methods include hysterectomy, bilateral salpingectomy and bilateral oophorectomy) or if they have missed a menstrual cycle.

^ During the COVID-19 restriction period, these assessments will not be completed at Visit 13 (week 48) and Visit 14 (week 60). All remaining assessments will be competed as per the protocol remotely via a telephone consultation (i.e. participants will not be required to attend the research clinic). Should the restrictions be lifted, participants can attend the research clinic and complete all procedures.

• During the COVID-19 restriction period, participants will not be seen at the research clinic for unscheduled and withdrawal visits. Should the restrictions be lifted, participants can attend the research clinic and complete all procedures.

Page 51 of 60

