16.2 Appendix 2 – Amendment History

Amendment No.	Protocol version no.	Date issued	Author(s) of changes	Details of changes made
SA05	7.0	11/09/2020	[name] [name] [name]	 Pharmacogenomics response analysis in subgroups determined by single nucleotide polymorphism (SNP) for alleles associated with the IL33/ST2 axis and baseline thoracic CT-derived % wall area are to be changed from subgroup objectives to exploratory outcomes for the following reasons: Due to COVID-19 there was a delay in transporting SNP samples to Genentech (San Francisco, California) and there were limitations for undertaking analyses in California and alternatively in Leicester. From March-June 2020, California was on a mandated shelter-in-place and shipment of samples to the USA was restricted. Genentech was only accepting samples for projects predetermined to be business critical, and COPD-ST2OP samples were not deemed business critical. Genentech was operating with a skeleton crew and therefore did not have adequate staff resource in place for sample testing and analysis, therefore causing a delay in obtaining the SNP data for the subgroup analyses. A large proportion of participants were unable to undergo their visit 13 CT scan due to COVID-19, therefore the CT scan data will take a smaller role in the analysis than originally planned and analysis of the baseline CT scan is affected by access to the University of Leicester campus due to COVID-19. The list of secondary and exploratory outcomes in the study summary has been tidied up to ensure consistency with the list of outcomes in section 3. The Trial Statistician and Senior Trial Manager have been added to the list of protocol contributors. For the subgroup objectives, it has been specified that the patient-reported outcome (PRO) and the lung function variable will be the St George's Respiratory Questionnaire for COPD patients (SGRQ-c) and forced expiratory volume in one second (FEV1) respectively.

Amendment No.	Protocol version no.	Date issued	Author(s) of changes	Details of changes made

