#### 2. Patient related outcomes (PROs) (Weeks 0, 4, 12, 24, 36 and 48)\*

- St George's Respiratory Questionnaire for COPD patients (SGRQ-c)
  - Total score\*
  - Domains (*post hoc*):
    - i. Symptoms score^
    - ii. Activity score^
    - iii. Impacts score^
- COPD Assessment Test (CAT)
- mMRC Dyspnoea Scale
- Visual analogue score (VAS)
  - o Total
  - o Dyspnoea
  - o Cough
  - Sputum production
- Sputum purulence colour card

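### The COVID-19 footnote drops the week-48 and week-60 questionnaires from visits that are held by telephone, so some week-48 patient-reported data are lost by rule

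*Protocol*

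**What the plan says.** The ^ footnote to the schedule of procedures (Protocol Appendix 1, repeated under SAP Table 1) reads: "During the COVID-19 restriction period, these assessments will not be completed at Visit 13 (week 48) and Visit 14 (week 60"). It continues: "All remaining assessments will be competed as per the protocol remotely via a telephone consultation". It ends with a relaxation: "Should the restrictions be lifted, participants can attend the research clinic and complete all procedures".

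In both schedules the mark sits on the V13 and V14 cells of SGRQ-c, mMRC, CAT, "VAS (dyspnoea, cough, sputum") and the sputum purulence colour card. Adverse events, concomitant medication, exacerbation frequency and the row "Participant Diary" have no mark at those visits.

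The outcome lists were not changed to match. SAP 2.2.1 still gives "Patient related outcomes (PROs) (Weeks 0, 4, 12, 24, 36 and 48"), as does Protocol 3.5.2. SAP 5.5.2 names SGRQ-C and CAT as two of its three key secondary outcomes, the third being post-bronchodilator FEV1. SGRQ-C is also the patient-reported outcome in the eosinophil subgroup analysis.

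**The concern.** The mark treats questionnaires like CT, spirometry, blood and sputum sampling, which cannot be done remotely. During restrictions, staff speak to the participant at week 48 and, as the schedule is written, do not collect health status. Protocol 11.1 groups questionnaires and diaries together as participant-reported source data, yet the diary is kept and the questionnaires are not.

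V13 is labelled the efficacy end point. Spirometry is unavoidably lost at a remote V13, so of the three key secondary outcomes only SGRQ-C and CAT could have been saved there. SAP 5.5.3 plans no sensitivity analysis for any secondary outcome, so the plan neither prevents the loss nor examines it.

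**Working it through.** The plan states no figure on this point, so there is none to reproduce. The check has four parts.

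**1. Which items need a clinic.**

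| Item at V13/V14 | Mark | Can it be done remotely? |
|---|---|---|
| CT, spirometry, body box, blood, sputum | ^ | No |
| SGRQ-c, CAT, mMRC | ^ | Questionnaires; no obstacle stated |
| VAS, colour card | ^ | Visual tools; need a posted form |
| Adverse events, medication, exacerbations | none | Yes, by telephone |
| Participant diary | none | Yes, retained |

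**2. Cost to a week-48-only contrast.** SAP 5.5.1 has an ANCOVA of change from baseline to week 48. Inputs are 80 randomised and 10% drop-out (Protocol 10.1), so 80 × 0.9 / 2 = 36 per arm. Let m be the share with no week-48 value (assumed).

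- n per arm = 36(1 − m)
- standard error factor = 1/√(1 − m)
- detectable difference in SD units (80% power, two-sided 5%) = (1.960 + 0.842) × √(2/n), before any gain from the baseline covariate

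| m | n per arm | SE factor | Detectable difference |
|---|---|---|---|
| 0 | 36 | 1.00 | 0.66 SD |
| 25% | 27 | 1.15 | 0.76 SD |
| 50% | 18 | 1.41 | 0.93 SD |

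**3. Cost to the pooled analysis.** The SAP 5.5.1 mixed model has treatment arm, the stratification factor, visit and a participant random effect. It lists no treatment-by-visit term, so its treatment effect pools visits. With a random intercept, intraclass correlation ρ, k post-baseline visits and total variance 1, each participant contributes information 1/(ρ + (1 − ρ)/k). A missed week 48 reduces k from 5 to 4.

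- ρ = 0.5: 1/0.600 = 1.667 with five visits, 1/0.625 = 1.600 with four. At m = 54% the average is 0.46 × 1.667 + 0.54 × 1.600 = 1.631, and √(1.667/1.631) = 1.011.
- ρ = 0.8: 1/0.84 = 1.190 and 1/0.85 = 1.176. At m = 13% the factor is 1.001.

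Over these assumed values the loss is 0.1% to 1.1%.

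**4. What is known about m.** No count of V13 questionnaires is given. For CT, which carries the same mark at V13, the amendment history (SA05) says: "A large proportion of participants were unable to undergo their visit 13 CT scan due to COVID-19". It also shows recruitment complete by 11 September 2019, so the last nominal week 48 (day 336) is 12 August 2020. Take uniform accrual ending on that date and restrictions lasting to the end of the visits. If they began at the SA03 issue date (27 May 2020), participants randomised after 26 June 2019 are affected: 77/213 days = 36% for 7-month accrual, 77/273 = 28% for 9-month. If they began in mid-March 2020 (assumed), the shares are 70% and 55%. If 9-month recruitment had instead ended on 28 May 2019, the mid to late March start gives only 13% to 16%. The documents do not choose between these.

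**The case against.** The strongest reply is that little is lost. The patient-reported outcomes have exactly the visit weeks that SAP 5.5.1 assigns to the mixed model. The ANCOVA best fits lung function, which is listed at weeks 0 and 48 only. On that reading the loss is about 1%. This stands, and it limits the size of the point. SAP 5.5.1 does not, however, confine the ANCOVA to lung function, and the SAP subgroup objective refers to change in SGRQ-C through 48 weeks. A week-48 contrast for these outcomes is therefore not excluded.

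Second, the change entered as an Urgent Safety Measure (SA03), no mode of administration is stated, and changing mode only at week 48 could disturb within-participant change. This partly stands. VAS and the colour card cannot simply be done on a call, and posting is a new procedure. It does not explain why SGRQ-C, CAT and mMRC stayed cancelled through SA04 and SA05. A mode effect would fall on both blinded arms.

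Third, clinic attendance could resume once restrictions lifted, so not every affected V13 need be lost. This stands.

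Fourth, a footnote edit comes too late. Protocol version 7.0 was issued on 11 September 2020, and SAP version 2.1 (2 December 2020) follows database lock. This stands for nearly all week-48 data and shifts the remedy towards reporting.

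**Conclusion.** The point holds in a limited form. The footnote, in both documents, cancels questionnaires at a visit that still takes place, with no reason given. The loss is confined to participants whose V13 fell in the restriction period and who did not attend later. It matters for a week-48-only contrast, where the standard error grows by 1/√(1 − m), and hardly at all for the pooled model. Both results rest on assumptions: m, the restriction dates and uniform accrual for the first, and the intraclass correlation for the second.

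A reader might infer more than the documents support:

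- **The primary outcome is damaged.** Exacerbation frequency is unmarked and continues by telephone.
- **The comparison is biased.** The rule acts by calendar date, not by arm, so no difference between arms is shown.
- **A large proportion of questionnaires is missing.** That statement concerns CT scans. It suggests that many V13 visits were affected but does not count questionnaires.
- **The whole patient-reported analysis loses these participants.** SAP 3.3 calls the modified intention-to-treat set complete-case, which might suggest this, but SAP 5.5.1 says the mixed model handles missing follow-up. That wording should be reconciled separately.

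**What to change.** For any visit still to come, and for any reuse of the remote-visit rule, in both schedules:

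- Remove ^ from SGRQ-C, CAT and mMRC at V13 and V14. Collect them by telephone or post within the visit window and record the mode.
- Collect VAS and the colour card by posted form.
- Add the same remote option to the separate footnote on unscheduled and withdrawal visits. Those cells carry a different mark, and that footnote only says that participants will not be seen in clinic.

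For visits already missed:

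- Report week-48 completeness of each patient-reported outcome by arm and by before or during restriction, and state that the schedule itself cancelled the assessment.
- Add a missing-data sensitivity analysis for SGRQ-C and CAT, labelled post hoc. SAP section 1 and SAP 6.2 allow for this if it is identified and justified. The controlled multiple imputation already cited for the primary outcome (SAP 5.4.3) is a natural starting point.

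The cost is footnote wording, postage, a field for mode, one table and one additional analysis. The downside is a possible small mode-of-administration effect at week 48, not expected to differ between blinded arms.
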